## 9. RESEARCH DESIGN AND METHODS

### Summary of design

A prospective, randomized, controlled, blinded trial to evaluate the comparative outcomes and effectiveness (clinical utility, perceived family utility, and cost effectiveness) of two methods of rapid genomic sequencing (WGS and WES) and two methods of analysis (singleton probands and familial trios) in acutely ill infants. Enrollment in this study includes enrollment into a Newborn/Infant biorepository and co-enrollment into the Genomic Biorepository: Protocol for the Collection, Storage, Analysis, and Distribution of Biological Samples, Genomic and Clinical Data (IRB #160468). Historic controls will be obtained from a separate retrospective chart review study following IRB approval.

Acutely ill infant inpatients who have an undiagnosed illness, and their families, will be eligible to participate in the study. We will enroll up to 1,000 infants. Locally, the study population will be recruited from Rady Children's Hospital (RCH) inpatient population, primarily the NICU, PICU and cardiovascular intensive care unit (CVICU), with a smaller population presenting to other hospital in-patient services. Recruitment will be targeted at the RCH main campus, but it may include referrals from satellite locations in the RCH network (particularly the RCH NICU network throughout San Diego County). All patients will continue to receive routine care as clinically indicated, including the state NBS and other genetic testing as determined by their treating providers. Half of the affected study participants will be randomized to receive rapid WGS and the other half will receive rapid WES. Each arm will initially be analyzed using the patient's (proband's) sample only. If a proband-only analysis fails to yield a diagnosis, genomic data from the biological family members (typically parents), when available, will be used to supplement analysis (trio analysis). Occasionally, a second affected sibling may be available for family analysis. Not infrequently, the father is not available for study. Similarly, we anticipate the need for targeted genetic analysis of biological parents, and possibly other family members, to confirm diagnostic results and/or provide additional information regarding inheritance.

### Recruitment, Enrollment and Sample Collection:

Enrollment will be sought within the first 96 hours following admission to RCH or an RCH network ICU or within 96 hours of meeting eligibility criteria for the study if the infant was not previously eligible. The clinicians will typically confirm study eligibility and make a referral to the research staff. The research staff

will approach the families and provide them with a brief summary of the study, including a study brochure (see appendix), research team contact information, and consent documents if requested. Families may also receive additional study information and potentially consent at the initial time or the study staff will leave the materials and follow up the next day. Families will be given the option to opt-out as a part of the study brochure, which may be given to the clinical staff or the research staff at any time. A decision to opt-out will require families to re-contact the research team directly should they change their minds.

Informed consent and permission will be sought for the patients and biological parents. Other family members, affected or unaffected, may be asked to enroll as well to assist with analysis. Other family members may include children or adults. Blood will be collected from patients and family members following informed consent. An order for “RCIGM Research Testing”, at no charge, will be placed in the medical record of each participant for sample collection and tracking purposes. The order will be marked as “Completed” at the conclusion of the analysis. A second clinical order will be entered, at no charge, for clinical confirmation of the research results. The results of the clinical confirmation will be entered into the affected child (or children if there are multiple affected individuals in one family) medical record(s) (see Return of Results below).

Following informed consent, subjects will have blood drawn for nucleic acid (DNA and possibly RNA) isolation at the time of enrollment in the study. All maximum blood sample volumes will be determined by the patient’s weight in a volume per kg calculation. A minimum of 0.5 ml (up to 3 ml) will be collected from the admitted patients by their clinical nursing staff when scavenged blood/DNA is not available. Volume will depend on the size of the patient and other clinical lab draw volumes at the time of collection. Up to 6 ml of blood will be collected from adult participants by trained research staff. Priority will be given to clinical lab samples over research samples. Buccal smears and saliva may be collected in addition to blood or in lieu of blood; heel-prick blood spots, additional blood, urine and left over fluid and tissue samples, if available, may also be collected and stored in the Rady Children’s Clinical Genome Center as part of the Genomic Biorepository (Study 160468). The latter samples will not involve invasive sampling, and are helpful for diagnosis in cases, for example, of mitochondrial diseases and somatic mutations. Samples scavenged from other clinical testing and/or other research studies (such as the RUB) will be determined based on the participant’s clinical presentation and symptoms. It is impossible to say at this time what amounts and sample types will be collected due to the large number of genetic diseases being studied.

We may collect additional samples for functional studies needed to confirm genetic results. The sample amounts, types and additional family members who may be requested to provide additional samples will be determined on a case-by-case basis. Whenever possible, previously obtained clinical samples and/or samples stored in the Genomic Biorepository and/or RUB will be scavenged to avoid unnecessary patient blood draws. If additional samples are required that are not available from other studies or left-over clinical samples, families will be contacted regarding these research-only additional samples. The specific sample type and amount will be discussed with each family and permission will be requested prior to any additional research-only sample collection. Additional samples that may be collected for research-only purposes include blood, buccal swabs, saliva, non-invasive stool collection, and/or a clean-catch urine specimen. The study team will coordinate collection of such samples, and whenever possible, will coordinate these collections to overlap with routine clinical care. No charges will be applied for research-only sample collection. We may also use non-invasive methods of DNA collection to test the sample accuracy against whole blood.

### **Randomization and DNA Analysis**

Patients and their family members who consent to participate will be randomized to receive either rapid Whole Genome Sequencing (WGS) or rapid Whole Exome Sequencing (WES). DNA will be extracted and rapid genomic sequencing will occur per Standard Operating Procedures within the Rady Children’s Clinical

Genome Center and in accordance with the Genomic Biorepository (Study 160468). Genomic data will be analyzed using the clinical features and symptoms as extracted from the patient's medical record, reported by clinicians, and/or by physical exam by research staff.

#### Stage One Analysis:

The initial symptom-driven analysis will be conducted on the patient's sample only (singleton analysis).

#### Stage Two Analysis:

If a diagnosis is not found promptly (within 24 hours) via a singleton analysis, the family (or any combination of parents and/or other family members) will be analyzed using the same technology that the patient was randomized to receive. Dependent upon logistics and the acuity of the patient's illness, we may generate trio genomic sequences simultaneously or in stages (singleton then parental duo).

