## **5. LAY LANGUAGE SUMMARY OR SYNOPSIS (no more than one paragraph)**

This study will seek to determine if rapid genomic sequencing improves outcomes for acutely ill infants. We will enroll up to 1,000 acutely ill infants in a prospective, randomized, blinded study to either rapid Whole Genome Sequencing (WGS) or rapid Whole Exome Sequencing (WES, which is 2% of the genome and ~2-fold less expensive). Outcomes will be measured both by objective clinical measures and family perceptions (patient/family centered outcomes). Primary analysis of WGS or WES will be in infants alone. Secondary analysis, in infants who do not receive a diagnosis, will be of families – ideally trios (mother, father and affected infant), which is ~2-fold more expensive. Trios will be analyzed within the same randomization arm (WGS or WES). This study is designed to quantify which acutely ill infants benefit from rapid genomic sequencing, by how much they benefit, how they benefit, which rapid genomic sequencing method is superior, and the cost effectiveness of such testing.

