## **6. SPECIFIC AIMS**

**Specific Aim 1.** Determine if, and by how, much rapid WGS is associated with better outcomes than rapid WES in acutely ill infants. The null hypothesis is that both tests are equivalent. This may occur, for example, if the diagnosis rate is similar or the additional diagnoses from WGS do not alter clinical management.

**Specific Aim 2.** Determine if and by how much rapid WGS is associated with better perceived outcomes in parents of acutely ill infants than rapid WES in acutely ill infants. The null hypothesis is that both tests are

equivalent. In addition, this will be the first study to examine the family-centered outcomes of rapid genomic sequencing, and particularly in Hispanic/Latino families.

**Specific Aim 3.** To compare diagnostic rates, time to diagnosis, and outcomes of rapid genome-wide sequencing compared with historical matched cases who received standard care before genome-wide sequencing was available. The null hypothesis is that genome wide sequencing does not increase diagnosis rate, time to diagnosis or outcomes.

**Specific Aim 4.** To compare diagnostic rates of singleton analysis versus familial analysis (ideally trio) and the cost-effectiveness of each testing method (rapid singleton WGS, rapid singleton WES, rapid trio WGS and rapid trio WES). The null hypothesis is that adding familial sequencing data does not significantly increase diagnostic yield.

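### Family data are opened after 24 hours without a singleton diagnosis, and no rule separates late proband-detectable diagnoses from those that needed relatives, so Aim 4's added yield may be inflated

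*Combined protocol and SAP*

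**What the plan says.** Section 9 describes two stages. Under Stage One Analysis, "The initial symptom-driven analysis will be conducted on the patient's sample only (singleton analysis"); no duration, end point or completeness rule is given. Stage Two Analysis opens with "If a diagnosis is not found promptly (within 24 hours) via a singleton analysis, the family" and then has relatives analysed with the technology to which the infant was randomized. It adds that "we may generate trio genomic sequences simultaneously or in stages (singleton then parental duo"), depending on logistics and acuity.

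Two other places give the trigger without a clock. The Summary of design in Section 9 says "If a proband-only analysis fails to yield a diagnosis, genomic data from the biological family members" are brought in, and that these "will be used to supplement analysis (trio analysis"). The synopsis in Section 5 says "Secondary analysis, in infants who do not receive a diagnosis, will be of families".

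Specific Aim 4 in Section 6 is "To compare diagnostic rates of singleton analysis versus familial analysis (ideally trio"), together with the cost-effectiveness of the four testing methods. It adds: "The null hypothesis is that adding familial sequencing data does not significantly increase diagnostic yield". On the analysis, the Data Analysis part of Section 9 has one sentence, which promises that the two rates will be analysed. It names no estimand, no test and no rule for assigning a diagnosis to a stage.

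**The concern.** Family data supplement the proband data, so the stage-two read contains everything that the stage-one read had, plus relatives' genotypes, more elapsed time and a second look. A variant that the analysts would have called from the infant's own data at, say, hour 30 would be called with family data already in use. If yield is tabulated by stage, that diagnosis counts as a gain from family data although relatives contributed nothing to it.

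This particular misattribution can only raise the added yield. It also cannot be cleanly undone later: once analysts have seen the parental data, nobody can establish what the proband-only read would have produced. The size of the familial gain is what Aim 4's cost-effectiveness comparison rests on, and Section 7 puts singleton testing at about half the cost of a trio. An overstated gain would make the trio look better value than it is.

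**Working it through.** **The plan's own figures.** There is none for Aim 4. The only power figure, 325 per arm in Section 10, concerns the clinical utility index for WGS against WES (50% against 40%). It reproduces as a one-sided test at 0.05 with 80% power and a continuity correction (325; two-sided without correction gives 388). Nothing below depends on it.

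**Inputs.** From the documents: the 24-hour trigger; up to 1,000 infants, 500 per arm; about 250 expected by September 2019. Not in the documents, so assumed:
- S, the singleton yield with no time limit: 30% to 50%.
- q, the share of those diagnoses made after 24 hours: 2% to 20%.
- f, the true gain from family data: 0 or 5 points.

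**Formula.** If diagnoses are counted by stage, apparent added yield = f + S × q.

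- Lowest combination: 30% × 2% = 0.6 points added to f.
- Middle: 40% × 5% = 2.0 points. With f = 0 the trial reports 2.0; with f = 5 it reports 7.0, which overstates the gain by 2/5 = 40%.
- Highest: 50% × 20% = 10 points.

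**What this does to a test.** The plan names no test, so take an exact McNemar test as an example. Family analysis follows only a negative singleton result, so discordant infants fall in one direction. With d of them the two-sided p is 2 × 0.5^d: d = 5 gives 0.0625 and d = 6 gives 0.031. Six infants are 0.6% of 1,000 or 1.2% of 500.

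Expected number of late proband-detectable diagnoses when f = 0 and S = 40%, with the binomial probability of at least six in brackets:

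| q | Points moved | 250 infants | 500 infants | 1,000 infants |
|---|---|---|---|---|
| 2% | 0.8 | 2 (0.016) | 4 (0.214) | 8 (0.810) |
| 5% | 2.0 | 5 (0.384) | 10 (0.935) | 20 (1.000) |
| 10% | 4.0 | 10 (0.937) | 20 (1.000) | 40 (1.000) |
| 20% | 8.0 | 20 (1.000) | 40 (1.000) | 80 (1.000) |

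A small late share could therefore produce a significant result with no true gain at full enrollment. At 250 infants and q = 5% it more often would not.

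**The case against.** A reader might infer that the plan ends the singleton read at 24 hours, credits everything later to the family, and so rejects Aim 4's null by construction. The documents do not support this. Stage Two Analysis says when family analysis starts. It does not stop the singleton read, and no section assigns credit by the clock. Rejection would require three things together: late proband-detectable diagnoses, counting by stage, and enough such cases.

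Other points also stand:
- **Net direction is uncertain.** When trio sequence is generated simultaneously, parental data may be in hand during the singleton read. If they informed it, singleton yield would rise and the familial gain would shrink. Targeted testing of relatives to confirm singleton results (Other Analysis, Section 9) works the same way, and missing fathers dilute the measured trio gain.
- **A difference by arm is speculative.** It is tempting to suppose that WGS data take longer to read than WES data, but no interpretation times are given.
- **The wording conflict is mild.** The synopsis and design summary can be read as short forms of the detailed rule.
- **Aim 4 is not the primary comparison.** Section 7 makes diagnostic yield a secondary outcome. It also says that de novo disease is far harder to find from the proband alone, so Aim 4's null is probably false in any case.

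The last point changes the emphasis more than the conclusion. If some gain is expected, its size is what matters, and size is what this ambiguity affects. Reading the three passages as compatible also leaves open which diagnoses count as singleton yield.

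**Conclusion.** The concern holds as a possible inflation of unknown size. The plan opens family data after 24 hours without a singleton diagnosis, compares singleton with family yield, and has nothing that separates extra time and a second look from the contribution of relatives' data. Counted by stage, Aim 4's added yield can be overstated. The illustration of 2 points, and the range of 0.6 to 10, rest wholly on assumed values for the singleton yield and the late share; the documents give neither. They also assume counting by stage, which the plan neither prescribes nor rules out. This is more than missing detail, because the information needed to attribute a diagnosis is lost once analysts see the parental data.

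**What to change.** Leave the trigger for opening family data unchanged and change only what is recorded and how diagnoses are counted.

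1. Before parental data are opened to the analysts, including when trio sequence was generated simultaneously, lock and time-stamp the singleton candidate list with its ACMG classification.
2. For each later diagnosis record (a) whether the variant was on the locked list and (b) whether its detection, or its classification as pathogenic or likely pathogenic, used relatives' genotypes.
3. Count a later diagnosis as singleton yield only if the variant was on the list **and** reaches pathogenic or likely pathogenic without any parental-genotype criterion. Joining these conditions with *or* would be wrong: it would credit to singleton both listed uncertain variants upgraded only by parental genotype and variants found only by trio filtering.
4. Count it as familial gain if relatives' data were needed for detection or classification.
5. Where a variant was not on the list, can be classified without parental data, and cannot be shown to have needed relatives for its detection, report it in a separate indeterminate group. Give the added yield with that group counted each way.
6. Report the 24-hour singleton yield separately.
7. Use one definition of singleton failure in the synopsis, the Summary of design and Stage Two Analysis.

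The cost is a wording amendment, a lock step and two fields on the analysts' form. The reported familial gain may be smaller, or may have to be given as a range. A completed second singleton read by analysts blind to family data would settle the indeterminate group, but it needs extra analyst time and is not essential.

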#### Other Analysis:

Some family members may have targeted sequencing and analysis done to confirm results and/or provide additional inheritance information of singleton analysis results.

Data analysis will follow the standards set by the clinical diagnostic laboratory and in line with recommendations from the American College of Medical Genetics (ACMG). Currently, a minimum of two expert data analysts will be responsible for analyzing the DNA variants following genomic sequencing. Analysts will be rotated among qualified RCIGM staff, including but not limited to laboratory directors, genetic counseling staff, trained medical and research staff. One of the analysts will then compile a report to be reviewed by the Molecular Pathology Laboratory Directors, [name] or [name], or the Medical Director, [name].

We anticipate that in rare cases a newborn may be so ill that the team lacks equipoise that the child can wait for the estimated ten day turnaround time of our send-out exome testing. In these rare cases, the PI, or his delegate, will decide if the child is not eligible for randomization. These children will remain in the research study throughout the entirety of the study, but they will receive in-house ultra-rapid whole genome sequencing by the RCIGM laboratory in lieu of either a rapid genome or rapid exome (both anticipated to be 10 day turn-arounds). For the purpose of study analysis, these subjects will be treated as excluded from randomization and analyzed as a separate category.

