### **Affected Participant Exclusion Criteria**

Inpatients of greater than 4 months of age, or who do not meet any of the inclusion criteria, or with:

1. Neonatal infection or sepsis with normal response to therapy
2. Isolated prematurity
3. Isolated unconjugated hyperbilirubinemia
4. Hypoxic Ischemic Encephalopathy with clear precipitating event
5. Previously confirmed genetic diagnosis that explains their clinical condition (i.e. have a positive genetic test)
6. Isolated Transient Neonatal Tachypnea
7. Permission is unable to be obtained by a legal guardian or court-appointed representative within 96

hours of becoming eligible for enrollment.

8. Nonviable neonates- newborns less than 28 days of life with a modified code status (only full code patients may be enrolled).

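### Aim 3 may drop the sickest sequenced infants through the separate-category rule, and the historical controls are not shown to meet matching conditions

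*Combined protocol and SAP*

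**What the plan says.** Section 9, under Other Analysis, foresees that "in rare cases a newborn may be so ill that the team lacks equipoise that the child can wait" for the expected turnaround of the send-out exome. In that event "the PI, or his delegate, will decide if the child is not eligible for randomization". No criterion is given. These infants stay in the study and receive in-house ultra-rapid genome sequencing instead of either randomised test. For study analysis, "these subjects will be treated as excluded from randomization and analyzed as a separate category". The sentence is not limited to any one aim.

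Aim 3 (section 6) covers diagnostic rates, time to diagnosis and "outcomes of rapid genome-wide sequencing compared with historical matched cases who received standard care before genome-wide sequencing was available". On the source of the comparators, the Summary of design in section 9 says: "Historic controls will be obtained from a separate retrospective chart review study following IRB approval". The documents give no matching variables, index date, control eligibility rules or adjustment method.

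Two enrolment rules also bear on who reaches the sequenced group. Section 9, under Recruitment, says "Enrollment will be sought within the first 96 hours following admission", or within 96 hours of meeting the criteria if the infant was not eligible before. Section 10 (exclusion 7) removes infants for whom permission is not obtained in that time. Exclusion 8 removes non-viable neonates, described as "newborns less than 28 days of life with a modified code status (only full code patients may be enrolled". Section 12 adds that neither samples nor clinical data are collected before consent.

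The Data Analysis text in section 9 lists QALYs, DALYs, mortality and severe morbidity as outcome measures. Sample size determination in section 10 calls QALYs saved a key primary outcome.

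**The concern.** Randomisation protects the comparison of genome with exome, and an infant who was never randomised has no place in it. Aim 3 has no such protection. Its exposure is rapid genome-wide sequencing, which the ultra-rapid infants received. Setting them apart in Aim 3 removes exposed infants because of how ill they were. The selection is an uncodified judgement made at the bedside, so a chart review has no means of removing the equivalent infants from the control side.

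The enrolment rules can act in the same direction. An infant who dies between becoming eligible and consent cannot enter the sequenced group. A chart-review control has no consent moment, so unless an index time is set, early deaths can be counted among controls only. The same applies to newborns with a modified code status if controls are not screened for it.

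At stake is whether a lower mortality or a QALY gain against historical care in Aim 3 could be read as an effect of sequencing.

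**Working it through.** **What there is to reproduce.** The plan gives no sample size, mortality rate or expected carve-out share for Aim 3. Its only calculated sample size, 325 per arm, concerns the clinical utility index for genome versus exome and does not bear on this point. The check below is therefore an illustration on stated assumptions.

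**Inputs**
- m, mortality without filtering: 10% (assumed), with 20% as an alternative. Section 7 cites about 20%, but for NICU infants with inborn errors of metabolism, not for the Aim 3 controls.
- q, mortality in the infants removed: 30-50% (assumed). As an upper value, 57% is the 100-day mortality (12 of 21) reported in section 7 for infants with a genetic diagnosis in an earlier study.
- f, share removed: 2% and 5% (assumed). The plan says only that such cases are rare.
- Group sizes: 250 (expected by the end of the supplement period) and 1,000 (the maximum), taken as equal in both groups.

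**Step 1: shift in mortality with no true effect.** If only the sequenced side loses these infants, its expected mortality is (m - f·q)/(1 - f).

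| f | q | Sequenced mortality (m = 10%) | Difference from 10% |
|---|---|---|---|
| 2% | 30% | (0.10 - 0.006)/0.98 = 9.6% | 0.4 points |
| 2% | 50% | (0.10 - 0.010)/0.98 = 9.2% | 0.8 points |
| 5% | 30% | (0.10 - 0.015)/0.95 = 8.9% | 1.1 points |
| 5% | 50% | (0.10 - 0.025)/0.95 = 7.9% | 2.1 points |

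In relative terms this runs from about 4% (0.4/10) to 21% (2.1/10).

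**Step 2: chance of a falsely significant benefit.** For a two-sided 5% pooled test of two proportions, ignoring matching, the chance is Φ((d - 1.96·s0)/s1). Here d is the difference from step 1, s0 the pooled standard error and s1 the unpooled one. With no bias it is 2.5% in this direction. Example: m = 10%, q = 40%, f = 5%, 1,000 per group gives d = 0.0158, s0 = 0.0129 and s1 = 0.0129, so Φ(-0.74) = 23%.

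| m | q | f | 250 per group | 1,000 per group |
|---|---|---|---|---|
| 10% | 40% | 2% | 4.2% | 6.7% |
| 10% | 40% | 5% | 8.9% | 23% |
| 10% | 57% | 2% | 5.5% | 10.9% |
| 10% | 57% | 5% | 16% | 50% |
| 20% | 40% | 2% | 3.2% | 4.2% |
| 20% | 40% | 5% | 4.8% | 8.6% |
| 20% | 57% | 2% | 4.0% | 6.2% |
| 20% | 57% | 5% | 8.0% | 19.7% |

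The 2% rows fit a carve-out that is truly rare. The 5% rows need either a commoner carve-out or the consent and code-status rules acting with it.

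**Step 3: effect of adding the infants back.** Sequenced mortality becomes (1 - f)·(m - f·q)/(1 - f) + f·q = m, so the difference due to the carve-out is zero. If the enrolment rules are also made equal on both sides, the difference from those rules is zero as well.

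**Step 4: diagnosis rate.** The same formula with an assumed overall yield of 40% and an assumed yield of 57% in those removed gives (0.40 - 0.02·0.57)/0.98 = 39.7% at f = 2% and (0.40 - 0.05·0.57)/0.95 = 39.1% at f = 5%. On these assumptions, removal works against sequencing.

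**The case against.** A reader might infer that the controls face none of these filters. The documents do not say so. They describe the controls as "historical matched cases who received standard care before genome-wide sequencing was available", drawn from a separate study whose protocol is not included here, and its rules may cover some of these conditions. What can be said is that this plan does not show it.

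Reporting a separate category hides nobody, and the text does not expressly leave these infants out of Aim 3. That is fair, but the rule is written for study analysis in general, and followed literally it takes them out of the sequenced group.

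The parenthesis on full code might be read as applying to every infant. The exclusion is framed for newborns under 28 days, while eligibility runs to 4 months. Likewise, survival to consent is implied by the 96-hour limit rather than stated, and consent may come well before 96 hours.

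The net direction is not settled either. Section 10 also excludes isolated prematurity, transient tachypnea, isolated unconjugated hyperbilirubinemia and infection responding normally to therapy. If controls were not screened for these, the sequenced group could look sicker, which would offset the tilt. This objection stands, and it is a further reason to apply every exclusion to both sides.

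A reader might also extend the point to Aim 1, supposing that infants could be moved after an exome allocation. The text speaks of not being eligible for randomisation and of a test replacing either randomised option, which reads as a decision before allocation. No flaw in Aim 1 is shown; only an explicit record is lacking.

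Finally, pooling ultra-rapid with the slower tests mixes test speeds. That is a real cost of the remedy and the reason to report both ways.

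**Conclusion.** The point holds for mortality, severe morbidity and QALYs in Aim 3. The separate-category rule, applied as written, removes sequenced infants chosen for severity, and the judgement behind it cannot be reproduced in chart-review controls. The consent and code-status conditions add to this to the extent that controls are not held to them, which the documents leave open.

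The size is unknown. With assumed mortality of 10% overall and 30-50% in those removed, the spurious difference is 0.4-0.8 percentage points if 2% are removed and 1.1-2.1 points if 5% are. A truly rare carve-out is therefore a small problem on its own. These figures assume that only the sequenced side is filtered and that no other exclusion offsets the effect.

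The point does not cover diagnosis rate or time to diagnosis. Setting aside the infants with the fastest test could lower the first and lengthen the second in those who remain. It also leaves the randomised comparison untouched. The matter is worth correcting because Aim 3 has no randomisation behind it and the correction is inexpensive.

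**What to change.** 1. Limit the separate-category rule to the genome-versus-exome comparisons (Aims 1 and 2) and the singleton-versus-trio comparison (Aim 4). Count the ultra-rapid infants in the Aim 3 sequenced group, and report Aim 3 with and without them.
2. Start the Aim 3 clock at the time eligibility was met, in both groups. Select controls who meet all the section 10 exclusions and who are alive and undiagnosed at the same elapsed time as the matched infant's enrolment. The permission rule has no counterpart in a chart review; being alive at the matched time takes its place.
3. State the matching variables and the control eligibility rules in this plan, or cite the chart-review protocol for them.
4. As a clarification only, record the carve-out decision with a time stamp before the allocation is opened, and analyse any infant moved after allocation in the assigned arm.

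The cost is wording in the analysis plan, one time stamp per infant and some extra work in selecting controls. The ultra-rapid infants remain in the study, so no additional recruitment is needed. The downside of item 1 is that test speeds are mixed in the main Aim 3 group, which the second report without those infants makes visible.
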